6.2 Secondary Endpoint(s)

- To determine the physical morbidity associated with lung cancer screening
- To determine the resource implications of screening and the resulting intervention
- To determine psychosocial consequences of lung cancer screening
- To assess the feasibility of population screening for lung cancer as reflected by uptake of invitations and compliance rates with annual screening
- Establish a blood and tissue bank for the future assessment of early detection diagnostics and novel tumour bio-markers.

6.3 UKLS Trial Design

[figure not shown]
[figure not shown]
The 'Wald Single Screen Design' has been chosen for the UKLS trial. The study arm is offered a single CT scan (with appropriate further workup where necessary), the control arm is given usual care, and both arms are followed up for lung cancer incidence and mortality. The details of this design are provided in Figure 1: UKLS Trial Design.

1. Individuals 50-75 years of age will be selected at random from NHS / SHA records and approached with an invitation letter, Participant Information Sheet and first questionnaire (Appendix A: Invitation Letter, Appendix B: Participant Information Sheet and Appendix C: first UKLS Questionnaire). The responses to the first UKLS questionnaire will be analysed, based on the Liverpool Lung Project [19] five year predictive risk model.
2. The high risk individuals will be contacted with a further second questionnaire (Appendix D: second Approach Letter, Appendix E: second Questionnaire, Appendix F Not Wishing to Participate and Appendix G: Participant Information Booklet) regarding specific questions on their medical history and also provided with detailed information about the UKLS Trial.
3. Individuals responding to the second questionnaire will be invited to one of the recruitment centres. They will be shown a UKLS Information DVD outlining the study in groups of 6-8 people. This will be followed by an informal group discussion with the chance to ask questions and gain further information. They will then meet with the Research Nurse and if the individual agrees to participate they will go through the consenting process.
4. After gaining fully informed written consent the Research Nurse will undertake a Lung Function Test. The recruit will also be asked to provide blood samples, buccal swab, nasal brushings and sputum specimens. The

recruit will also be asked to complete a touch screen lifestyle/medical history questionnaire and a baseline psychosocial and health economics questionnaire. All smokers will be provided with smoking cessation advice sheets and a list of local NHS Stop Smoking services.

5. The recruits will then be randomised into either CT screen group or the control group.
6. In total 4,000 individuals will be recruited into the Pilot UKLS trial with 2,100 randomised into the screened group. In total 32,000 individuals will be recruited into the main UKLS trial with 16,000 randomised into the screened group.
7. Participants will then complete follow-up psychosocial and health economics questionnaires two weeks after being notified of their CT results, or notification that they are on the control arm of the trial.

Figure 1: UKLS Trial Design

7 STUDY POPULATION

7.1 Inclusion Criteria

1. Risk criteria based on the LLP Risk Prediction Model (includes age, sex, smoking duration, history of previous pneumonia, history of previous cancer, family history (early/ late onset) exposure to asbestos – algorithm)
2. Males and females aged between 50 to 75 years old
3. Fully informed written consent given

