4.2 Rationale

The objective of the UKLS trial is to assess whether LDCT screening and treatment of early lesions will decrease lung cancer mortality compared to a control group without screening. Additionally, a UK trial would aim to test the intervention against the criteria outlined by the UK Screening Committee, especially those concerning cost effectiveness. A useful aid to cost-effectiveness is the ability to select a population at sufficiently high risk to give a substantial harvest of tumours in return for the screening activity. The group selected should also be of sufficiently high risk that the benefits of the screening will outweigh the likely harms.

The most efficient way of controlling cost will be to screen only those individuals who are at high risk of developing the disease. There has been increasing interest in developing methods for individual risk prediction for lung cancer. Models have been developed for use within high risk groups [15], and for the general population [16], based mainly on age and smoking. The predictive accuracy of lung cancer risk models may be further improved by the addition of other epidemiological risk factors [17]. The Liverpool Lung Project (LLP) [18] has recently developed a method to calculate absolute risk of lung cancer over a defined period, based on age, sex,

smoking duration, family history of lung cancer, history of non-pulmonary malignant tumour, history of pneumonia and occupational exposure to asbestos [19]. The LLP risk questionnaire has been validated in the Harvard case control, then EUELC case control and the LLP cohort studies. The LLP risk model has distinctive strengths. Firstly, the predictor variables are all explicitly defined and can be readily assessed at the time of patient presentation and secondly, patients can be assigned to their appropriate risk class on the basis of information from the initial history alone.

The screening process confers potential harms as well as potential benefits. In a randomised trial and in any future national screening service, the screening would be provided only to those whose risk was sufficiently high that the likely benefits outweigh the likely harms.

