6.1 Primary Endpoint(s)

- To establish the impact of pre-clinical detection of lung cancer lung cancer mortality by comparing lung cancer mortality between the control group and the screened groups combined
- To establish if there is a lung cancer mortality benefit from CT screening
- Establish total mortality benefit
- Cost effectiveness of a national lung cancer screening programme

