7.2 Exclusion Criteria

1. Unable to give consent
2. Co morbidity which would unequivocally contraindicate either screening or treatment if lung cancer were detected
3. A CT scan of the chest performed within one year of the invitation to be screened
4. Any condition precluding written informed consent
5. Inability to lie flat
6. Weight greater than 200 kg (too large for CT scanner)

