14.2 Follow up

All participants randomised onto the UKLS trial will be registered with either the National Health Service Central Register for England and Wales (ONS) or the Cancer Registry. The computerised randomisation for each subject at the registry will be tagged for prompt notification to the study directors in the event of new cases of cancer and deaths from cancer in the study population. The registry will also notify the LCTU of individual subjects who do not appear on the register so that further information required to trace their entry, can be obtained or alternative methods of follow up can be employed.

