15.2 Sample Size

The sample size/power calculations had the aim of determining a screening schedule which would optimise when and with what study size a significant result is likely in UKLS, with respect to the comparison of lung cancer mortality in the intervention and control group. The question of particular interest is whether a study offering only a single screen to the study group, or one offering multiple screens, is likely to be more efficacious in terms of:

- (1) how soon a significant result can be expected; and
- (2) resources expended on screening

Without actually carrying out the full trial, the timing and magnitude of the effect on mortality, if any, cannot be known for certain. We can, however, arrive at estimates using published data on the following quantities:

- The incidence of lung cancer in the target population
- Uptake of screening
- The mean sojourn time (MST) of asymptomatic lung cancer (i.e. the duration of the window of opportunity for asymptomatic detection) and its inverse, the rate of progression from asymptomatic to symptomatic disease
- Sensitivity of the screening test, CT scanning
- Survival of asymptomatic lung cancer cases, possibly taking into account length bias/over diagnosis

- Survival of symptomatic lung cancer cases

Single screen design

Although we shall use estimates of instantaneous rates of transition (e.g. from asymptomatic to symptomatic disease, from alive to dead), we shall convert these to discrete time probabilities, to obtain simple deterministic models. Let:

I = Annual incidence rate of lung cancer in target population

λ_1 = Instantaneous rate of transition from asymptomatic to symptomatic disease (=1/MST)

λ_2 = Instantaneous death rate from lung cancer of asymptomatic cases

λ_3 = Instantaneous death rate from lung cancer of symptomatic cases

S = sensitivity of the screening test

We assume a uniform annual incidence and exponential rates of progression to symptomatic disease and death [25]. We first demonstrate how to estimate the cumulative death rates in intervention and control groups for the simple case of a single screen study. In the intervention group, at time point 0, the expected rate of detection of asymptomatic lung cancers in those attending for screening is:

$$P = \frac{IS}{\lambda_1}$$

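### No criterion excludes lung cancer diagnosed before randomisation, and the primary endpoint does not leave out deaths from it, so the mortality rate ratio is diluted to an unknown, probably modest extent

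*Protocol*

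**What the plan says.** **Eligibility.** Inclusion criterion 1 (Protocol 7.1, repeated in the section 3 summary) rests on the LLP risk model and lists among its inputs "history of previous pneumonia, history of previous cancer, family history (early/ late onset) exposure to asbestos". Section 4.2 describes the same model as using "history of non-pulmonary malignant tumour, history of pneumonia and occupational exposure to asbestos". Section 7.2 has six exclusions, and none names lung cancer as a past or current diagnosis. Two could remove some such people: exclusion 2, "Co morbidity which would unequivocally contraindicate either screening or treatment if lung cancer were detected", and exclusion 3, "A CT scan of the chest performed within one year of the invitation to be screened".

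**Checks before randomisation.** The second questionnaire asks about medical history and serves to establish the inclusion and exclusion items (6.3, 8.1). The nurse confirms eligibility at the clinic (8.2), and the database checks it again (8.3).

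**Endpoint.** The first primary endpoint in 6.1 is assessed "by comparing lung cancer mortality between the control group and the screened groups combined". Section 14.2 arranges notification "in the event of new cases of cancer and deaths from cancer in the study population". Section 15.5 plans Poisson regression on cumulative lung cancer mortality and says that a full analysis plan is still being developed.

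**Sample-size model.** Section 15.2 builds the study-arm deaths from two sources: cancers detected at time 0, through "the expected rate of detection of asymptomatic lung cancers in those attending for screening", and symptomatic cancers arising later. Control-arm deaths come from symptomatic cancers arising during follow-up.

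**The concern.** A fit person treated for lung cancer some years ago, with no chest CT in the year before invitation, meets no exclusion. That person can reach the risk threshold on age, smoking duration, pneumonia, family history or asbestos, whether or not the earlier lung cancer scores. If the cancer later proves fatal, nothing in 6.1, 14.2 or 15.5 stops the death from counting.

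Such a death says nothing about pre-clinical detection, because the cancer was already diagnosed. It is equally likely in either arm, so it adds the same expected number to both counts: the rate ratio is diluted and the variance grows, while the planned numbers assume no such deaths. In the CT arm, residual or recurrent disease seen on the scan would also enter the detection, sensitivity and lead-time estimates of 15.5, which are meant to describe newly detected asymptomatic disease.

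**Working it through.** **Planned figures first.** Table 1 (15.2) gives, at year 3, cumulative lung cancer mortality of 5.3 (study) and 7.8 (control), taken as per 1,000, with 16,000 per group for 90% power at two-sided 5%. The standard two-proportion formula needs 21,878 per group for 90% power at these rates, and 16,343 for 80%. Power at 16,000 per group is 79%. The 90% claim is therefore not reproduced. That is a separate sample-size matter; here 79% is only the starting point against which dilution is measured.

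Expected deaths: 0.0078 × 16,000 = 124.8 (control) and 0.0053 × 16,000 = 84.8 (study). Ratio 84.8/124.8 = 0.68; z = 40/√209.6 = 2.76; power = Φ(2.76 − 1.96) ≈ 79%.

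**How many people could be affected.** The protocol gives no prevalence of earlier lung cancer, so I derive a pool from its own parameters, I = 0.007 per year and λ₃ = 0.56 per year, assuming a steady state:

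- All living diagnosed cases: I/λ₃ = 0.007/0.56 = 12.5 per 1,000, or 200 per 16,000.
- More than one year from diagnosis: 12.5 × e^(−0.56) = 7.14 per 1,000, or 114 per 16,000.

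The second pool fits the case at issue better, because exclusions 2 and 3 should remove many recent cases.

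**Assumptions.** These people join at 5% to 20% of the rate of others (my assumption; the documents offer no figure). Their lung cancer death hazard lies between 0.07 and 0.56 per year, the protocol's values for screen-detected and symptomatic disease. The upper value is severe for people fit enough to be recruited.

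The three-year death probability is q = 1 − e^(−3h): 0.189 at h = 0.07 and 0.814 at h = 0.56. Extra deaths per arm are k = 114 × joining rate × q. Then RR = (84.8 + k)/(124.8 + k), z = 40/√(209.6 + 2k) and power = Φ(z − 1.96).

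| Joining rate | People per arm | Hazard | Extra deaths per arm (k) | RR | Power |
|---|---|---|---|---|---|
| none | 0 | – | 0 | 0.68 | 79% |
| 5% | 5.7 | 0.07 | 1.1 | 0.68 | 78.5% |
| 5% | 5.7 | 0.56 | 4.6 | 0.69 | 77% |
| 20% | 22.8 | 0.07 | 4.3 | 0.69 | 77% |
| 20% | 22.8 | 0.56 | 18.6 | 0.72 | 72% |

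The absolute difference stays at about 2.5 per 1,000 throughout.

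**Sensitivity to prevalence.** Setting the proportion with earlier lung cancer directly, with the same two hazards: 0.1% gives RR 0.69 to 0.71 and power 78% to 74%; 0.2% gives RR 0.69 to 0.74 and power 77% to 70%. The 20% joining rate above corresponds to 22.8/16,000 = 0.14%.

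**The case against.** **The risk item.** A reader might infer from 7.1 that earlier lung cancer itself counts as qualifying risk. The documents do not support that. Criterion 1 is based on the LLP model, its bracket abbreviates that model's inputs, 4.2 defines the cancer item as non-pulmonary, and 8.1 says that the database algorithm follows the model. What stands is an inconsistency of wording. The missing exclusion does not depend on it.

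**The recruitment pathway.** The second questionnaire, the nurse and the database may catch these people, and the questionnaire appendix is not available to check. But each of these steps, as described, tests eligibility against the listed criteria, and a questionnaire item does not create an exclusion that 7.2 lacks. The psychosocial plan in 14.3 even names personal experience of lung cancer as a predictor. That phrase is too loose to prove that such people are expected, but it does not suggest that they are barred.

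**The analysis plan.** Which deaths count could be defined in the analysis plan, which is not at hand. This has force: silence on the derivation rule alone would not be a finding. Eligibility, however, belongs in the protocol, and the protocol's endpoint and its own sample-size model do not cover the same deaths.

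**Size and direction.** One could take the whole pool of 200 per 16,000, the 20% joining rate and the hazard of 0.56, and so reach about 33 extra deaths per arm, RR 0.75 and power 67%. That counts people within a year of diagnosis, many of whom exclusions 2 and 3 should remove, and gives fit survivors the mortality of newly diagnosed symptomatic disease. It overstates the case. It is also fair to say that the effect is conservative: it cannot create an apparent benefit of screening.

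**Conclusion.** The gap is real. As written, the protocol admits people with lung cancer diagnosed before randomisation and does not leave their lung cancer deaths out of the primary endpoint, although 15.2 plans only for cancers found at or after the screen. The direction is clear: the rate ratio moves towards 1, variance rises, and the absolute difference is essentially unchanged.

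The size cannot be fixed from the documents. Under the stated assumptions it runs from negligible to a loss of about seven percentage points of power. It depends mainly on the assumed joining rate and on how fast such people die of their disease. This is a moderate to low issue, worth correcting because the correction is cheap, and not a threat to the validity of the comparison.

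**What to change.** 1. Add to 7.2 and to the summary an exclusion for any lung cancer diagnosed before randomisation, by self-report on the second questionnaire and checked through the registry linkage already planned in 14.2. It should refer to diagnosed disease only, since undiagnosed prevalent cancer is what the scan is meant to find.
2. In 7.1 and the summary, restrict the cancer-history item to non-pulmonary malignant tumours, as in 4.2, and confirm that the database algorithm is coded that way.
3. State that the primary endpoint counts only deaths from lung cancer diagnosed after randomisation. Apply one rule, based on date of diagnosis, to both arms without reference to allocation.

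The cost is a line of text, possibly one questionnaire item if it is not already there, a date filter on linked data and the loss of a few recruits. The planned sample size does not change on this account.

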7.2 Exclusion Criteria

1. Unable to give consent
2. Co morbidity which would unequivocally contraindicate either screening or treatment if lung cancer were detected
3. A CT scan of the chest performed within one year of the invitation to be screened
4. Any condition precluding written informed consent
5. Inability to lie flat
6. Weight greater than 200 kg (too large for CT scanner)

7.3 Patient Withdrawal from Trial Intervention

In consenting to the trial, participants are consenting to all trial procedures, follow-up and data collection. If voluntary withdrawal from intervention occurs, the participant should be asked to allow for the LCTU to keep information on them that has been collected and stored.

Participants may be withdrawn from treatment for any of the following reasons:

- a. Participant withdraws consent.
- b. Intercurrent illness preventing further treatment or follow-up.
- c. Any change in the participant's condition that justifies the withdrawal of the participant in the clinician's opinion.

If a participant wishes to withdraw from trial treatment, centres should nevertheless explain the importance of remaining on trial follow-up or, failing this, of allowing routine follow-up data to be used for trial purposes. Generally, follow-up will continue unless the patient explicitly also withdraws consent for follow-up.

7.4 Withdrawal from Trial Completely

Participants who autonomously withdraw from the trial for reasons other than those listed above, have previously consented to follow-up in the trial. Data up to this time can be included. They may need to reaffirm that they consent to follow-up through usual NHS mechanisms. If the participant explicitly states their wish not to contribute further data to the study, the LCTU should be informed in writing by the responsible physician and an end of study CRF should be completed.

7.5 Loss to Follow-up

If any of the study participants are lost to follow-up, contact will initially be attempted through the PI at each centre. If this is unsuccessful, the patient's GP will be asked to provide follow-up information to the recruitment centre. This will be described in the Participant Information Booklet and consent obtained.

7.6 Co-enrolment Guidelines

Participants registered onto UKLS are not restricted to enter any other clinical trials or studies.

8 Enrolment and Randomisation

8.1 Screening

Potential participants will be invited to take part in the trial from the age/sex registers of Health Authorities (HAs) geographically related to the collaborating centres. Local HAs will be contacted during the set-up phase of the trial for permission to access their registers. This will ensure that invitations to participate in the trial can be sent to the correct age groups. Inviting un-biased cohorts of people is central to the trial design, as uptake needs to be documented in order to comprehensively answer the questions of whether a national lung cancer screening programme is feasible.

The enrolment plan has been discussed in detail with the PCTs. The preferred plan will be for HAs to provide details of participants (name, address, NHS number and GP details) electronically to Radar, the data management organisation that will send participants the invitations and questionnaires.

The process of invitations begins with Radar sending the first questionnaire to selected participants.

The initial information packs will include:

- Invitation letter
- Participant information sheet
- First questionnaire
- Refusal questionnaire
- Pre-paid envelope to send completed documents back to Radar

If the HAs provide contact details of eligible participants in electronic format, the data will be imported to the Radar database. Each participant on the list will be automatically allocated a random seven digit unique number which will be their own unique reference number for the life of the trial.

Once the initial invitation and questionnaire have been sent out to the potential participants, the data from these questionnaires will be returned to Radar using the pre-paid envelopes. Radar will use postcodes to compute Index of Multiple Deprivation (IMD) scores of all approached participants and send this IMD data along with their age, gender and unique 7 digit identifying number to the UKLS team. Radar will scan the questionnaire data and send the data to the LCTU and it will be imported into the UKLS database. The Risk Algorithm, based on the LLP risk model will be built into the UKLS database and will check which participants are 'high risk' according to the selection criteria and thus eligible for the trial.

Participants with a high risk score and have expressed an interest in participating in lung screening, will receive a second information pack. The second information pack will be sent by Radar (which will elucidate inclusion/exclusion parameters) and will include:

- Second Invitation Letter
- UKLS Patient Information Booklet (PIB)

- Second questionnaire
- Refusal questionnaire
- Pre-paid envelope to send completed documents back to Radar

The replies are returned to Radar, where the questionnaires will be scanned and the information on eligible participants sent to the LCTU and imported in the UKLS database. The participants that respond to the specific inclusion/exclusion criteria questions and indicate an interest in lung screening will be invited to attend the local pilot recruitment centre.

8.2 Recruitment

In the pilot study, recruitment will take place at two centres, Liverpool Heart and Chest Hospital and Papworth Hospital. The main trial will have seven recruitment centres; the remaining five are still to be selected. As detailed above, if the participants respond positively to the second approach, the UKLS project management team, in conjunction with the recruitment centre, will invite them to a 'Recruitment Centre' for a 'Clinic Visit' which will consist of the following:

- Recruits in groups of 6-8 individuals will be shown a UKLS Information DVD (Appendix H: UKLS DVD Outline) which provides a background to the UKLS trial, its design and objectives, randomisation, CT screening, investigations, Care Pathways and the translational studies. The research nurse will hold a group discussion to answer general questions.
- The participant will then proceed to a separate clinic room, where they will meet with the UKLS research nurse to confirm eligibility for the study and to discuss any outstanding issues of the trial in detail. The participant has the opportunity to ask questions at this stage
- If an individual agrees to participate, fully informed written consent to participate in the UKLS study will be taken by the UKLS Research Nurse. (Appendix I: UKLS Informed Consent Form)
- The UKLS Research Nurse will then perform the following:
 - a. Lung Function Test assessed by the Research Nurse (FEV1/ FEC recorded)
 - b. Phlebotomy; all participants will have up to 24mls of blood taken at the registration visit. Blood samples, buccal swabs, nasal brushings and sputum samples will be labelled as detailed in the SOP, and packaged. The packages will be collected on a daily basis by courier for delivery to the University of Liverpool Experimental Cancer Medicine Centre (LECMC) Good Clinical Laboratory Practice (GCLP) laboratory.
 - c. 24 mls of blood will also be collected from participants referred to the Multi-Disciplinary team prior to surgery or investigation as well as at subsequent out-patient follow up visits. These samples will be transported to the University of Liverpool Cancer Research Centre, [name], Liverpool.
- The participant will then be asked to complete a Touch Screen computer lifestyle, medical history, psychosocial and health economics questionnaire. Assistance will be provided to the participants on how to complete the questionnaire.
- Approximately 2 weeks after the clinic visit, participants will be informed to which arm they have been randomised. All smokers will be provided with

smoking cessation advice sheets and a list of local NHS Stop Smoking services.

